# 7. PHARMACOKINETIC ANALYSES

At the visits specified in the Schedule of Activities (Section 9), venous blood samples will be collected from all patients, for a total of 5 scheduled samples per patient, to determine the plasma concentrations of MP-101 and its primary active metabolite LY2812223. The sparse sampling scheme in Table 2 will be used. The scheduled time for the 2 to 4 hour assessment was changed from Week 8 to Week 10 in Amendment b of the protocol. The concentration data will be summarized according to the time interval, ignoring differences in week or visit collected.

Week	Visit	Sample Collection Time Intervals
2	4	4 to 8 hours post-dose
4	5	Pre-dose and 0 to 2 hours post-dose
6	6	8 to 12 hours post-dose
8/10	7/8	2 to 4 hours post-dose

#### Table 2: Plasma Pharmacokinetic Sampling Scheme

The actual sample collection date and time (24-hour clock time) must be recorded, as well as the actual date and time of the 2 most recent doses. If a patient discontinues early, a sample should be taken at the early termination visit, if possible. Additional PK samples may be collected at additional time points during the study.

In the case of unscheduled PK samples or samples taken at the early termination visit, the actual time from the last dose to the PK sample will be calculated and the concentration assigned to the appropriate time interval.

The plasma concentrations of MP-101 and LY2812223 will be summarized using descriptive statistics: n, mean, standard deviation, coefficient of variation, minimum, median, maximum, geometric mean, and geometric coefficient of variation. In addition, the following figures will be created:

 Plots of individual QTcF absolute values (γ-axis) versus plasma drug concentrations (x-axis). Separate figures for MP-101 concentrations and LY2812223 concentrations.

Different symbols will be used to denote the dose level the patients were on at the time of the PK assessment. The least-squares regression line of QTcF versus concentration will be added to the plot, by dose level if there are a sufficient number of patients at more than one dose level. All data points will be included in a single plot.

- 2) Plots of individual change from baseline QTcF values (y-axis) versus plasma drug concentrations (x-axis). Separate figures for MP-101 and LY2812223 concentrations. Different symbols will be used to denote the dose level the patients were on at the time of the PK assessment. A least-squares regression line of QTcF versus concentration will be added to the plot, by dose level if there are a sufficient number of patients at more than one dose level. All data points will be included in a single plot. This plot will be similar to the plot of absolute QTcF values versus concentration.
- 3) Plots of individual screening eGFR values (y-axis) versus individual average of dose normalized plasma drug concentrations (x-axis). Separate figures for MP-101 and LY2812223 concentrations. For each patient, all concentrations will be dose normalized and averaged; that is, the concentration will be divided by the dose the patient was on at the time of the assessment, and all the dose-normalized concentrations will be averaged. This resulting average concentration value will be plotted; all data points will be included in a single plot.
- 4) [For the safety interim analysis only.] Plot of individual plasma drug concentrations (y-axis) as a function of time from last dose (x-axis). Separate figures for MP-101 and LY2812223 concentrations. All dose groups overlaid and uniquely labelled.

- a. For the interim analysis, there should be 3 assessments for each patient, which will be plotted at the following mid-points of the nominal time intervals: 0 = Visit 5/pre-dose values, 1 = Visit 5/0-2hr post-dose value, 6 = Visit 4/4-8hr post-dose value. All assessments from all patients will be included on the same figure, but the patients will not be differentiated. Different symbols will be used to denote the dose level the patients were on at the time of the PK assessment.
- b. For the final analysis, the data will be evaluated using population PK/PD modeling techniques, by a vendor approved by the Sponsor. Data from this study may be combined with data from previous studies to develop the model.

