7.4. Dose Titration

Figure 7.1 illustrates the dose titration schedule.

[figure not shown]

Figure 7.1. Dose titration schedule for protocol MP-101-01.

At Visit 2 (Week 0), patients will be randomized to the MP-101 arm or the placebo arm. All patients will start at a dose of 20 mg or equivalent placebo (Figure 7.1). If intolerance is reported at a dose of 20 mg between Visit 2 (Week 0) and Visit 3 (Week 1), the patient will be discontinued from the study. Intolerance is defined as the inability to tolerate TEAEs such as dizziness, nausea, and vomiting, which in the opinion of the investigator are possibly related to MP-101.

At Visit 3 (Week 1), the dose of MP-101 (or equivalent placebo) will be increased to 40 mg. If intolerance is reported at a dose of 40 mg between Visit 3 (Week 1) and Visit 4 (Week 2), the patient will be discontinued from the study.

At Visit 4 (Week 2), the dose of MP-101 (or equivalent placebo) will be increased to 60 mg. If intolerance is reported at a dose of 60 mg between Visits 4 (Week 2) and 5 (Week 4), the patient will be asked to return for an unscheduled visit for down-titration to 40 mg. Patients down-titrated to 40 mg prior to Visit 5 (Week 4) will remain at this dose for the remainder of the study.

At Visit 5 (Week 4), the dose of MP-101 (or equivalent placebo) will be maintained at 60 mg. If intolerance is reported at a dose of 60 mg at Visit 5 (Week 4), the patient will be down-titrated to 40 mg and will remain at this dose for the remainder of the study. If intolerance is reported at a dose of either 40 mg or 60 mg beyond Visit 5 (Week 4), the subject will be discontinued from the study.

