8.2. Discontinuation from the Study

Patients may be discontinued in the following circumstances:

- enrollment in any other clinical trial involving an investigational product or enrollment in any other type of medical research judged not to be scientifically or medically compatible with this study
- participation in the study needs to be stopped for medical, safety, regulatory, or other reasons consistent with applicable laws, regulations, and good clinical practice (GCP)
- investigator decision
 - o the investigator decides that the patient should be discontinued from the study
 - o if the patient, for any reason, requires treatment with another therapeutic agent that is intended for the treatment of psychosis, discontinuation from the study occurs prior to introduction of the new agent
- patient decision
 - o the patient and/or caretaker requests patient withdrawal
- sponsor decision

If a patient discontinues the study early, the site will make every reasonable effort to have the patient return for an early termination visit to have end-of-study procedures performed as shown in the Schedule of Activities (Section 2). If the patient does not return, this will not be considered a protocol deviation.

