9.5. Pharmacokinetics

9.5.1. Pharmacokinetic Sampling

At the visits and times specified in the Schedule of Activities (Section 2), venous blood samples will be collected from all patients, for a total of 5 scheduled samples per patient, to determine the plasma concentrations of MP-101, and its primary active metabolite LY2812223. The sparse sampling scheme in Table 9.1 will be used.

Table 9.1.	Plasma Pharmacokinetic Sampling Scheme
------------	--

Week	Visit	Sample Collection Time Intervals
2	4	4 to 8 hours postdose
4	5	Predose and 0 to 2 hours postdose
6	6	8 to 12 hours postdose
10	8	2 to 4 hours postdose

The actual sample collection date and time (24-hour clock time) must be recorded, as well as the date and time of the 2 most recent doses. If a patient discontinues early, a sample should be taken at the early termination visit, if possible.

Samples are to be collected at specific time intervals relative to dose administration; therefore, visits that include timed PK testing (Visits 4, 5, 6, and 8 [Weeks 2, 4, 6, and 10, respectively]) must be scheduled relative to the patient's dosing schedule. During Visit 5 (Week 4), the first PK sample will be taken predose; the dose will be administered and another PK sample will be taken up to 2 hours postdose. For all visits that include PK sampling, the approximate start and stop times of food consumption prior to dosing and up to 4 hours postdose will be recorded.

Additional PK samples may be collected at additional time points during the study if warranted and agreed upon between both the investigator and sponsor.

Instructions for the collection and handling of blood samples will be provided by the sponsor.

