## **1.4.** Sample Size Determination

Approximately 100 patients will be enrolled to enable approximately 80 evaluable patients to complete the study through at least Visit 5 (Week 4).

The primary analysis will use a one-sided Fisher's exact test with a 5% type 1 error rate.

If the NPI response rate in MP-101 treated patients is 30% greater than in placebo treated patients (65% vs 35%), with 40 evaluable patients per treatment group there is at least an 80% chance (i.e. Power) that MP-101 will demonstrate superiority to placebo.

The sample size was calculated assuming an expected 20% drop-out rate of patients in each arm prior to Week 4, so that 100 patients are planned to be enrolled to arrive at 40 patients/arm (N=80) in the Evaluable population.

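### The SAP's eGFR plot averages all of a patient's dose-normalised concentrations whatever the time since the last dose, so patients with few or late samples are not comparable with completers

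*SAP*

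**What the plan says.** SAP section 7 summarises plasma concentrations by time interval. Table 2 gives Pre-dose (no hours attached), 0-2, 2-4, 4-8 and, last, "8 to 12 hours post-dose". Samples outside the schedule are placed by elapsed time: "In the case of unscheduled PK samples or samples taken at the early termination visit, the actual time from the last dose" is computed and the concentration goes to whichever interval suits. Nothing is said about a sample later than 12 h that is not a trough, and no sample is excluded.

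The third figure in that section plots screening eGFR against one exposure value per patient. "For each patient, all concentrations will be dose normalized and averaged"; for the normalisation, "the concentration will be divided by the dose the patient was on at the time of the assessment". Time since dose plays no part.

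Protocol 9.5.1 supplies the ET samples: "If a patient discontinues early, a sample should be taken at the early termination visit, if possible". Protocol 8.2 says only that "the site will make every reasonable effort to have the patient return for an early termination visit"; the schedule gives the ET visit no day or window. SAP 1.4 plans for an "expected 20% drop-out rate of patients in each arm prior to Week 4".

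Protocol 7.4 discontinues patients who do not tolerate 20 mg in the first week or 40 mg in the second. The first scheduled PK sample is at Visit 4 (Week 2).

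**The concern.** Concentration over a once-daily dosing interval depends strongly on when the sample is drawn. An average over five spread-out times and a single late value measure different things, even after division by dose. In this figure the difference in sampling pattern appears as a difference in exposure.

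Patients who leave for intolerance at 20 or 40 mg will generally have no scheduled PK sample, so any point they contribute rests on the ET sample alone. If that sample is a trough or later, they are plotted at the low-exposure end whatever their true exposure. If leaving is related to eGFR, the mixture also distorts the pattern the figure is meant to show. This is the SAP's only display of exposure against renal function, in a trial that admits patients down to eGFR 45.

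The by-interval summary has a smaller version of the problem. A sample at 36 or 48 h fits no interval, and if it is put in Pre-dose for want of another place, it lowers that row.

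**Working it through.** **The plan's own counts.** Table 2 gives 1 (Visit 4) + 2 (Visit 5) + 1 (Visit 6) + 1 (Visit 7/8) = 5 samples, as stated. The numeric intervals cover 2 + 2 + 4 + 4 = 12 of the 24 h between doses. SAP 1.4 implies 20% of 50, or about 10, MP-101 patients leaving before Week 4. How many leave before Visit 4 or give an ET sample is not stated.

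**Inputs.** For LY2812223, Protocol section 3 gives a half-life of about 11 h and a steady-state tmax of about 4 h, both from healthy men. Assumed: a one-compartment curve, half-lives of 8 to 20 h as a range, and ET samples at 24 to 72 h. Sampling times are interval midpoints (1, 3, 6, 10 h), with Pre-dose at 24 h. No half-life is given for MP-101, so these figures do not cover it.

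**Curve.** At time t after the last dose at steady state,

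C(t) ∝ exp(-kt)/(1 - exp(-24k)) - exp(-ka·t)/(1 - exp(-24ka)),

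with k = ln2/11 = 0.063 per h, and ka = 0.536 per h so that tmax is 4 h. As a fraction of Cmax:

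| Hours | 1 | 3 | 6 | 10 | 24 | 36 | 48 | 72 |
|---|---|---|---|---|---|---|---|---|
| C/Cmax | 0.704 | 0.979 | 0.953 | 0.771 | 0.321 | 0.151 | 0.071 | 0.016 |

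Completer's average: (0.321 + 0.704 + 0.979 + 0.953 + 0.771)/5 = 0.746.

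**Points plotted for patients who leave early, against 0.746:**

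- Lone ET sample at 24 h: 0.321/0.746 = 0.43, so 57% low (36% to 69% over half-lives of 20 to 8 h).
- Lone ET sample at 48 h: 0.071/0.746 = 0.095, so about 90% low (72% to 96%).
- Visit 4 plus ET at 24 h: (0.953 + 0.321)/2 = 0.637, about 15% low.
- Visit 4 plus ET at 48 h: (0.953 + 0.071)/2 = 0.512, 31% low (28% to 31%).
- Visit 4 alone, no ET sample: 0.953/0.746 = 1.28, so 28% high. The shift follows the sampling pattern and is not always downward.

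**Pre-dose row.** If 5 samples at 48 h join 40 true troughs, the geometric mean is multiplied by (C48/C24)^(5/45) = 0.220^(1/9) = 0.845, a fall of about 16% (9% to 21%). ET samples at 24 h leave it unchanged.

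**Effect on the picture.** Simulation: 50 patients, eGFR uniform on 45-95, and k = (ln2/11) × (eGFR/90) × exp(N(0, 0.3)), following the mainly renal elimination assumed in Protocol 5.5. There are ten leavers, five with an ET sample only and five with Visit 4 plus ET. Low-eGFR leavers are those with the smallest eGFR + N(0, 15). Mean Spearman correlation of eGFR with plotted exposure:

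| | ET at 24 h | ET at 48 h |
|---|---|---|
| No leavers | -0.57 | -0.57 |
| Leavers at random | -0.52 | -0.46 |
| Low-eGFR leavers | -0.41 | -0.21 |

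If all ten leavers have only a 48 h ET sample, the values are about -0.40 (random) and -0.05 (low eGFR).

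**The case against.** The strongest objection is that a reader might infer that ET samples are off-drug samples, and the documents do not say so. The SAP's one convention, in the exposure part of section 6.1, puts the last dose on the day before each drug accountability visit. The schedule marks ET as such a visit, so the sample would fall near 24 h: a trough, which belongs in Pre-dose. One drawn within 12 h of a dose fits a numeric interval. This stands, and it limits the size. Later samples are still foreseeable. Protocol 7.6 discontinues patients who miss more than 5 consecutive days at 60 mg, which can put the ET sample beyond 120 h. Visit 3 is a telephone call, so a patient leaving then must make a separate trip. The 57% gap at 24 h needs no off-drug sample at all; it comes from averaging unequal sets of times.

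A reader might also call the divisor undefined once dosing stops. Zero cannot be meant, and the last dose level is the natural reading, so this needs a clarification only.

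The simulation is generous: all ten expected leavers return and give a sample, though sampling is only if possible. With four leavers at 48 h, chosen at random, the correlation is about -0.52. No passage says that low-eGFR patients leave more often. The 11 h half-life may be short here; at 22 h, which the model implies at eGFR 45, a lone 48 h sample is about 69% low (0.263/0.842 = 0.31).

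Finally, the figure carries no test or regression line, and Protocol 10.3.5 assigns the effect of renal function to population PK. That stands in full.

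**Conclusion.** The point holds as a minor one. Read as written, the rule for the eGFR plot puts single-sample and five-sample patients on one axis and mixes sampling time with exposure. Table 2 also has no place for a sample well after the last dose except an undefined Pre-dose.

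The size depends on ET timing, which the documents do not give. Near 24 h the effect on the overall picture is modest; at 48 h or later it is larger, most of all if leaving is related to eGFR. These figures rest on the one-compartment curve, the healthy-volunteer half-life and the assumed number of ET samples.

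The effect is confined to the descriptive eGFR figure and the by-interval summary. Population PK can use the recorded times, and efficacy results and error rates are untouched. A reader might infer that the Assessment Committee would be misled at the interim. SAP section 3 says only that interim displays are a subset of the final ones and does not name this figure, so that is not supported. Nor do the documents show that intolerance goes with high exposure.

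**What to change.** In SAP section 7:

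1. Replace the all-sample average with eGFR plotted against dose-normalised concentration within a common interval, for example one Pre-dose panel and one 4-8 h panel.
2. Normalise by the last dose taken before the sample.
3. Define Pre-dose as about 20-28 h after the last recorded dose.
4. List later samples separately and keep them for population PK, but leave them out of the by-interval summary and the plot. Say the same for any sample between 12 and 20 h, which would still have no interval.

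An ET sample near 24 h is then compared with completers' troughs, like with like.

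This is a cheap improvement: a few SAP sentences and one changed figure. No new data are needed, since sample times and the two most recent dose times are already recorded. The downside is that patients with only a late sample appear in a listing and not in the figure, and each panel holds only patients sampled in that interval.

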The primary treatment effect will be measured as the difference in the percentage of patients with a response on either the NPI-Psychosis or Agitation/Aggression subscales at the end of the treatment period. A patient with a 30% improvement from baseline on a subscale will be considered a responder for that subscale. A patient with a psychosis diagnosis at screening will be considered an overall responder with a response on the NPI-Psychosis subscale, a patient with a diagnosis of agitation/aggression at screening will be considered an overall responder with a response on the NPI-Agitation/Aggression subscale, and a patient with both diagnoses will be considered an overall responder with a response on either subscale. The primary analysis will use a one-sided Fisher's exact test with a 5% type 1 error rate. The primary population for analysis will include all randomized patients who take at least 1 dose of double-blind study treatment and complete Visit 5 (Week 4) with NPI efficacy data (i.e., the Evaluable population).

The primary analyses will be performed with patients grouped by treatment arm (i.e., MP-101 or placebo) regardless of their final dose level.

2. Schedule of Activities

Schedule of Activities for Protocol MP-101-01

	Screen	Treatment Period (10 Weeks)			Follow- up					
Visit Number	V1	V2	V3a	V4	V5	V6	V7a	V8	V9	ET
Week	-1 to -5	0	1	2	4	6	8	10	11	
Days from Randomization (target)	-1 to-35	0	7	14	28	42	56	70	77	
Visit Window (± days from target)				2	2	2		2	2	
Study site visit	Х	Х		Х	Х	х		х	Х	Х
Informed Consent										
(before any procedures/tests)	X									
Clinical Assessments										
Demographics, height	X									
Weight	Х	Х		X	X	Х		Х	Х	X
Vital signs (BP and pulse)	Х	х		X	Х	Х		Х	Х	Х
Medical history and physical exam	Х									
Neurological exams	X	X						X		X
TUG (if applicable)	X	X		X	х	X		X	Х	
Concomitant medications	X	X	х	X	X	X	Х	X	X	X
Inclusion/exclusion review	X	xb	A		A			- 1	- 1	
Hepatitis B surface antigen,	Α	Α-								
Hepatitis C antibody, HIV	X									
Randomization		X								
Investigational product dispensing				v	v	v				
Dose administration at site		X		X	X	X				
Investigational product		X		X	X					
accountability				X	X	X		X		X
Symptom directed physical exam		v		v	v	v		v	v	v
Habits (alcohol, caffeine, nicotine,		X		X	X	X		X	X	X
tobacco)	X	X	X	X	X	X	X	X		X
Safety Measures										
Adverse event assessment	37	37		37		v		v	37	N/
	X	X	X	X	X	X	X	X	X	X
C-SSRS ^c	X	X		X	X	X		X	X	X
Single 12-lead ECG	X	X		X	X			X	X	X

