9.4.3. Electrocardiograms

For each patient, a single 12-lead digital ECG will be collected according to the Schedule of Activities (Section 2) and the provided study-specific recommendations.

Electrocardiograms should be recorded before collecting any blood for safety or PK tests, when possible. Patients must be supine for approximately 5 to 10 minutes before ECG collection and remain supine but awake during ECG collection. Electrocardiograms may be obtained at additional times, when deemed clinically necessary. All ECGs recorded should be stored at the investigational site.

Electrocardiograms will be interpreted by a qualified physician (the investigator or qualified designee) at the site as soon after the time of ECG collection as possible, and ideally while the

patient is still present, to determine whether the patient meets entry criteria at the relevant visit(s) and for immediate patient management, should any clinically relevant findings be identified.

If a clinically significant finding is identified (including, but not limited to, changes in QTcF from baseline) after enrollment, the investigator will determine if the patient can continue in the study. The investigator or qualified designee is responsible for determining if any change in patient management is needed, and must document_his/her review of the ECG printed at the time of collection. Any new clinically relevant finding should be reported as an AE.

Any clinically significant findings from ECGs that result in a diagnosis and that occur after the patient receives the first dose of the investigational product, should be reported to Mediti Pharma, Inc., or its designee, as an AE via CRF.

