9.5.2. Bioassay

Human plasma samples will be analyzed for MP-101 and LY2812223 using a validated liquid chromatography-tandem mass spectrometry method at a laboratory approved by the sponsor. Samples will be collected from all patients, but only samples from patients taking MP-101 are planned to be assayed.

Bioanalytical samples collected to measure investigational product concentrations will be retained for a maximum of 2 years following last patient visit for the study. During this time, samples remaining after the bioanalyses may be used for exploratory analyses such as metabolism and/or protein binding work.

Drug concentration information that may unblind the study will not be reported to investigative sites or blinded personnel until the study has been unblinded.

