10.3. Statistical Analyses

10.3.1. General Statistical Considerations

Statistical analysis of this study will be the responsibility of Mediti Pharma, Inc. or its designee.

Details of the summarization and analysis of the clinical trial data will be described in the SAP, which will be finalized prior to database lock.

The primary analyses will be performed with patients grouped by treatment arm (i.e., MP-101 or placebo) regardless of their final dose level.

The sample size was calculated assuming a 20% drop-out of patients in each arm, and assuming that early withdrawal is not influenced by the treatment effect. Secondary and supportive analyses may be performed to explore the effect of early withdrawal on the primary endpoint.

Pharmacokinetic analyses will be conducted on data from all patients on MP-101. Safety analyses will be conducted for all treated patients, whether or not they completed all protocol requirements.

Additional exploratory analyses of the data will be conducted as deemed appropriate.

A change to the data analysis methods described in the protocol will require an amendment only if it changes a principal feature of the protocol. Any other change to the data analysis methods described in the protocol or SAP, and the justification for making the change, will be described in the clinical study report.

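### The QTcF-versus-concentration lines in SAP 7 mix concentration with visit, because they use no visit or patient term and, in effect, no placebo ECGs

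*SAP*

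**What the plan says.** SAP 7 plans two QTcF figures for each analyte (MP-101 and LY2812223). Figure 1 plots absolute QTcF and figure 2 plots change from baseline, both against plasma concentration. For figure 2, "A least-squares regression line of QTcF versus concentration will be added to the plot", split by dose level if numbers allow; figure 1 gets the same kind of line. For both, "All data points will be included in a single plot". The SAP names no visit, time or patient term and says nothing about placebo patients in these figures.

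Protocol 9.5.2 says that samples are drawn from everyone but "only samples from patients taking MP-101 are planned to be assayed". Protocol 10.3.1 adds: "Pharmacokinetic analyses will be conducted on data from all patients on MP-101".

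Sampling is sparse, "for a total of 5 scheduled samples per patient", and each window is fixed to a visit (Protocol Table 9.1):
- V4: 4 to 8 h postdose
- V5: "Predose and 0 to 2 hours postdose"
- V6: 8 to 12 h postdose
- V8: 2 to 4 h postdose

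In the Schedule of Activities (Protocol section 2), the row "Single 12-lead ECG" is marked at V1, V2, V4, V5, V8, V9 and early termination, for both arms. V6 is not marked. On ECG timing, Protocol 9.4.3 says: "Electrocardiograms should be recorded before collecting any blood for safety or PK tests, when possible".

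**The concern.** A line fitted to QTcF against concentration invites the reader to take its slope as a drug effect. That is safe only if nothing else that moves QTcF varies with concentration. Here the schedule makes concentration vary with visit: the predose trough comes only at V5, while V4 and V8 are sampled near the 4-hour tmax given in Protocol section 3. A QTcF difference between V5 and V4/V8 that has nothing to do with the drug would therefore appear as a slope. The randomised placebo arm has ECGs at the same visits and could separate the two, but as written it does not enter.

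These lines are the only regression of QTcF on exposure that the SAP specifies. A biased line could suggest a concentration-QT relation that is absent, or flatten one that is present. Correct ECG-to-sample pairing alone does not remove this, because the confounding is with visit.

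**Working it through.** **The plan's own figure.** The plan gives no number for these lines. The sample count reproduces: 1 (V4) + 2 (V5) + 1 (V6) + 1 (V8) = 5. Since V6 has no ECG, at most 1 + 2 + 1 = 4 of the 5 share a visit with an ECG, and the two V5 samples share one ECG.

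**Bias formula.** Let the QTcF change be y = βc + s, where c is concentration and s is a change also present on placebo. The least-squares slope then has expectation β + Σ(c − c̄)(s − s̄) / Σ(c − c̄)². The second term is the bias. It is zero when s is the same at every visit.

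**Concentrations.** The inputs from Protocol section 3 are a half-life of about 11 h and a tmax of about 4 h.
- Assumed profile: one compartment at steady state, 24 h dosing, the same dose at every visit.
- k_e = ln 2 / 11 = 0.063 per h.
- k_a = 0.644 per h, from ln(k_a/k_e)/(k_a − k_e) = 4.

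Concentrations at window mid-points, as fractions of Cmax:

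| Point | c | c − c̄ (c̄ = 0.740) |
|---|---|---|
| V4, 6 h | 0.928 | 0.188 |
| V5, predose | 0.306 | −0.435 |
| V5, 1 h | 0.735 | −0.005 |
| V8, 3 h | 0.992 | 0.252 |

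Σ(c − c̄)² = 0.288.

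**Bias with no true drug effect (mid-points, no variability).**
- *Constant +5 ms:* bias 0. The intercept is 5, so the line sits 5 ms too high with nothing subtracted for placebo.
- *Linear drift 0 / 2.5 / 5 ms over V4 / V5 / V8:* 2.5 × (0.252 − 0.188) / 0.288 = about 0.6 ms per Cmax. The reverse drift gives −0.6.
- *QTcF 5 ms lower at V5 than at V4 and V8:* 5 × (0.188 + 0.252) / 0.288 = about 7.7 ms per Cmax. The opposite sign gives −7.7.

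The drift result depends on the V4 point being near the full-dose level. The dose steps up to 60 mg only at V4, so lower V4 concentrations would give drift more weight.

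**With between-patient variability.** When exposure and sampling times vary, concentration spreads within each visit and the bias shrinks. Simulations with 40 MP-101 patients and no drug effect gave:

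| Assumed shared V5 shift | Mean false slope per Cmax | Assumptions |
|---|---|---|
| 3 ms | 2.1 to 2.6 ms | change SD 14 ms, ICC 0.5 |
| 5 ms | 3.5 to 4.4 ms | change SD 14 ms, ICC 0.5 |
| 5 ms | 3.4 ms | between- and within-patient SD 8 ms each; exposure log-SD 0.35 |

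In the last setting, a mixed model adding placebo at concentration 0, arm, a visit/time factor and a random patient intercept gave a mean slope of −0.2 ms, which is near zero.

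**Patient effect.** With no shared shift in that same setting, the pooled fit's standard error averaged 2.1 ms against an actual spread of 2.6 ms. Leaving out the patient term therefore mainly overstates precision.

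**The case against.** The strongest reply is that these are lines drawn on descriptive plots. No slope test, interval, threshold or decision rule is attached to them, and QT is not a named objective or endpoint. SAP 6.5 already summarises QTcF change by treatment group at each time point and counts extreme values, so a shift shared with placebo would be visible there. SAP 7 also plans population PK/PD modelling at the final analysis, and Protocol 10.3.5 allows safety measures to be explored against concentration. Protocol section 3 reports no significant QTc changes in earlier studies at doses up to 400 mg.

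Much of this stands, and it rules out several stronger readings that a reader might infer:
- *Any QTcF change shared by both arms is read as a drug effect.* It is not. The intercept takes up a constant change, and only change that lines up with the high- and low-concentration visits matters.
- *The plan carries an inflated false-positive rate.* Testing the pooled slope at a one-sided 5% level gives positive results in roughly 22 to 26% of null trials for a 3 ms shift and 40 to 43% for 5 ms (change SD 14 ms, ICC 0.5). No such test is planned, so these figures show only how misleading a line can look.
- *The V5 ECG is a morning predose reading and the others come later in the day.* The documents fix the time of the PK sample, not of the ECG. The ECG precedes blood collection only when possible, and on-site dosing is scheduled at V4 as well as V5.
- *The SAP excludes placebo.* It does not say so. The exclusion is inferred from the protocol, though the SAP gives no instruction to enter placebo ECGs at zero.

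What the reply does not do is correct the slope. The by-arm summaries leave the line as drawn, and the PK/PD plan specifies neither a QTcF model nor how placebo is handled.

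**Conclusion.** The concern holds in a limited form. The slope of the QTcF lines in SAP 7 is confounded with visit, and possibly with time of day. Shared QTcF change that differs between V5 and V4/V8 biases it upward or downward. For an assumed shared V5 shift of 3 to 5 ms, the false effect at peak is about 2 to 4 ms once patient variability is allowed for.

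That size is illustrative only. It rests on an assumed shift pattern, assumed variances, a simple one-compartment profile at constant dose, and the V5 ECG values entering with both V5 samples. The documents give no QTcF variance or placebo drift, so they do not show that such a shift will occur. The mechanism does not depend on those numbers: it follows from the fixed link between window and visit and from the terms missing from the fit. This is a worthwhile, inexpensive improvement to a safety display and does not touch the primary efficacy analysis.

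**What to change.** In SAP 7:

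1. **Figure 2.** Replace the least-squares line with a linear mixed model for change in QTcF. Fixed effects are concentration, treatment arm, nominal visit and baseline QTcF; add a random patient intercept. Enter placebo ECGs from the same visits at concentration 0, which needs no assay.
2. **Pairing rule.** State which sample each ECG is paired with. V5 has two samples and one ECG. V6 has a sample and no ECG, so it drops out. Say also how early-termination ECGs and samples are handled.
3. **Reporting.** Give the slope and the placebo-corrected predicted change in QTcF with a 90% CI at a defined concentration, such as the geometric mean in the 2 to 4 h window.
4. **Figure 1.** Show it as a scatter without a line, or label its line descriptive and confounded with visit.

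The cost is SAP wording and a short model program. No visits, assays or patients are added, since ECGs are already scheduled in both arms. The reported slope SE becomes slightly wider: about 3.7 against 3.0 ms at peak in the simulation with change SD 14 ms. The 3.0 understates the pooled slope's actual spread of about 3.8, so little real precision is lost.
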